## **List of Abbreviations**

*For example: LIST OF ABBREVIATIONS-list alphabetically.*

**AE:** Adverse event

**DCC:** Data Coordinating Center

**DMC:** Data Management Center

**DM:** Diabetes Mellitus

**DMS:** Data Management System

**DSMB:** Data Safety Monitoring Board

**FCP:** Fecal Calprotectin

**SCD:** Specific Carbohydrate Diet

**MSD:** Mediterranean Style Diet

**PPRN:** Patient-Preferred Research Network

## Study Summary

Title	Randomized, Multicenter, Comparative Effectiveness Trial of Specific Carbohydrate and Mediterranean Diets to Induce Remission in Patients with Crohn's Disease
Short Title	DINE-CD
IRB Number	825907
Phase	N/A
Methodology	Open Label Randomized Clinical Trial
Study Duration	3 years
Study Center(s)	Multicenter trial of up to 50 sites
Objectives	
Primary:
 

1. To compare the effectiveness of the Specific Carbohydrate Diet and a Mediterranean style diet to induce symptomatic and clinical remission in patients with Crohn's disease.

2.

 
Secondary:
 

1. To compare the effectiveness of the Specific Carbohydrate Diet and a Mediterranean style diet to reduce mucosal inflammation in patients with active Crohn's disease. Mucosal inflammation will be assessed by measuring the concentration of calprotectin in the feces (FCP).

2. To compare the effectiveness of the Specific Carbohydrate Diet and a Mediterranean style diet to reduce systemic inflammation in patients with active Crohn's disease. Systemic inflammation will be assessed by measuring the concentration of C reactive protein (CRP).

3. To compare the effectiveness of the Specific Carbohydrate Diet and a Mediterranean style diet to improve the following symptoms in patients with Crohn's disease: a) fatigue, b) pain, c) joint symptoms.

4. To determine the proportion of patients who continue the study diets when prepared food is no longer provided without cost and the reasons for discontinuation of the diets.

Number of Subjects	194 participants to be enrolled across all sites

**Main Inclusion and Exclusion Criteria**

*Inclusion Criteria:*

- Age ≥18
- Documented diagnosis of Crohn's disease
- sCDAI >175 and <400
- Access to a computer with internet and the ability to complete daily online surveys
- Capable of providing consent to participate

*Exclusion Criteria*

- Pregnancy
- Hospitalized patients or surgery planned within 6 weeks
- Ostomy or known symptomatic intestinal stricture
- Use of the Specific Carbohydrate Diet within 4 weeks of screening
- Start or change\* dose of thiopurines, natalizumab, vedolizumab or methotrexate(w/in 12 weeks) or anti-TNF or ustekinumab (w/in 8 weeks) of screening
- Start or change\* in dose of any 5-ASA medication within 2 weeks of screening
- Use of antibiotics within 2 weeks of screening
- Start or change\* corticosteroids within 1 week of screening or dose >20mg prednisone or equivalent
- Baseline stool frequency >4 bowel movements/day when well
- BMI<16 or ≥40
- Celiac disease, recent c diff colitis, or diabetes
  - Albumin<2.0mg/dl (if measured as part of routine clinical care)  
\* Exception for treatment failures: if a subject is determined to fail on any of the following standard lines of treatment at the treating investigator's discretion, subjects may screen for study intervention based upon the following wash out periods: 4 weeks for thiopurine and methotrexate and 8 weeks for natalizumab, vedolizumab, anti-TNF, or ustekinumab.

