## **3 Investigational Plan**

### **3.2 General Design**

This is a randomized, multicenter, comparative effectiveness trial of SCD and MSD to induce remission in patients with Crohn's Disease. Participants will be screened for eligibility criteria and if eligible, enrolled into the trial. Participants will continue on the diet to which they are randomized for 6 weeks with all food being provided to the participant during this time period. Participants will complete brief daily online surveys throughout their entire study participation, from consent to week 12. These will be used to calculate scores for the Short Crohn's Disease Activity Index (sCDAI). The primary outcome will be assessed at week 6 at an in-person visit. From weeks 7 to 12 participants will be asked to adhere to their randomized study diet on their own. At week 12 participants will be evaluated at an in-person visit.

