The following screening and baseline data will be collected: participants' height, weight and vital signs, their medical history, diet history, their symptoms and any medication they may be taking. Their blood will be drawn to measure hsCRP and hematocrit levels. At some sites, two additional tubes of blood may be drawn for plasma. A physical exam will be done to obtain CDAI score. Participants will collect a stool sample no more than 28 days prior to start of the study diet and no more than 28 days after the date of initial consent (either in verbal or written form). Female participants will be asked to take a urine pregnancy test. Participants' charts will be reviewed and abstracted to obtain information for eligibility. One 24-hour dietary recall will be completed after the screening visit prior to start of the study diet. A dietitian from the University of Pennsylvania will contact the participant to complete this. The participant will complete daily online surveys regarding their Crohn's disease symptoms in order to calculate an sCDAI score. Participants will also be instructed about these online surveys they will receive throughout the study and when to collect stool samples.

The participant will ship their stool sample to [name] lab at the University of Pennsylvania. Penn will send an aliquot of stool to LabCorp to measure FCP. Remaining sample will be aliquoted and stored in the biobank managed by the CCF. See *section 7.8 Stool Processing for more information*.

The participant must complete 5 to 7 days of sCDAI symptom recording (the daily online surveys) before randomization and the start of study diet. They should not complete the 5-7 days of sCDAI symptom recording more than 14 days prior to start of study diet. Also, the participant must complete 5-7 consecutive days of sCDAI symptom recording no more than 14 days after nominal eligibility is determined.

Medical records may need to be requested for potential participants identified through CCFA Partners who are not already a patient at one of the participating clinic sites. Only the medical records necessary to determine eligibility should be requested. The Data Coordinating Center will provide a medical records release form for sites to use.

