sCDAI: A minimum of 5 and maximum of 7 days of patient reported symptoms will be required to compute the sCDAI to determine eligibility. The participant will accomplish this via daily online surveys sent to the participant after at least a verbal consent is obtained. The sCDAI is computed using the following equation where  $L$  is the number of liquid or very soft stools,  $A$  is the rating of abdominal pain (0-3, none to severe),  $W$  is the rating of general wellbeing (0-4, generally well to terrible),  $n$  is the day of follow-up, and  $d$  is the number of days of data used to compute the sCDAI.

$$sCDAI = 44 + \frac{7}{d} * \left( \left( 2 * \sum_{n=1}^d L \right) + \left( 5 * \sum_{n=1}^d A \right) + \left( 7 * \sum_{n=1}^d W \right) \right)$$

Stool Collection: The participant must collect a stool sample no more than 28 days from the date the participant will start the study diet and no more than 28 days after the initial form of consent. Participants at the University of Pennsylvania may bring the sample with them to visit 1. All other participants must ship the sample to the University of Pennsylvania in materials the DCC ships to the participant's home. *See section 7.8 Stool Processing for more information.*

Diet History Questionnaire (DHQ): The participant will complete an online Diet History Questionnaire at home prior or immediately following the visit in the clinic. Alternatively, the participant may complete it at their visit if a computer with internet is available. It will take approximately 30 minutes to complete. The DMS will email the participant the link to the questionnaire as well as their username and password to access the questionnaire.

24-hr Dietary Recall: A dietitian from the University of Pennsylvania will call the participant at home to ask them what they ate the day before. This should be completed on a random day between screening and the start of study diet.

FCP: Upon receipt of the stool sample, laboratory staff at the University of Pennsylvania will send a small amount of the sample to LabCorp for a baseline measurement of FCP. LabCorp will report the results to the Data Coordinating Center (Penn).

Blood draw: one tube of blood will be drawn for measuring hsCRP and one for hematocrit. Two additional tubes may be drawn for plasma collection. Blood tubes and other collection materials will be

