## **6.5 Subject Withdrawal**

Participants may withdraw from the study at any time.

Participants may be withdrawn at the discretion of the investigator prior to randomization for the following reasons:

- Failure to provide the baseline stool sample
- Failure to complete at least 5 of the 7 baseline sCDAI surveys

Participants will be withdrawn from the study if they experience worsening symptoms requiring a change in their Crohn's disease treatment, the initiation of an antibiotic for gastrointestinal symptoms, and/or an increase of greater than 10mg/day of prednisone or equivalent for a non-gastrointestinal condition\*.

*\*Please see section 6.2.2 for equivalency chart*

Participants who have been randomized to one of the two diets and withdraw early from the study should complete an end of study visit and provide a stool sample at the time of withdrawal as described in section 6.2.5.

If the participant wishes to discontinue the study diet early for reasons not related to worsening Crohn's Disease (e.g., they don't like the diet), they will be asked to remain in follow-up and complete the next in-person visit at the target date of that visit (either week 6 or week 12). This will be the end of study visit.

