**Change from baseline stratified by treatment arm:** For continuous outcome measures, such as sCDAI, PRO2, PRO3, and FCP, we will compare the week 6 and week 12 values to the baseline value using the Wilcoxon sign rank test, a nonparametric paired test. These analyses will be conducted separately for each treatment group. Imputation of missing data for this analysis will assume the worst case scenario that the outcome measure was worse during follow-up than at baseline. (Note that approach to missing data for other analyses are described below).

**Approach to missing data (PCORI Methodology Standard MD1-5):** Our study design will minimize missing data by requiring participants to continue to provide data and samples in order to continue to receive the study diets without cost. In addition, we will employ reminder methods that were developed in our current CCFA Partners RCT and will collect symptoms daily, but have documented that less frequent data collection is adequate. It is possible that missing follow-up data will be more common among participants who did not have reduced symptoms, particularly those whose symptoms worsened. There are several approaches to missing data in clinical trials. Complete case analysis violates the principle of

intention to treat and as such will not be employed. For continuous measures, last observation carried forward (LOCF) is the most commonly used, but it is not necessarily the most conservative. Baseline observation carried forward (BOCF) may be more appropriate, particularly in circumstances where the outcome would be expected to return to the baseline level if the treatment is discontinued. The European Medicines Agency recommends picking the most conservative approach depending on the individual trial, favoring a responder analysis (i.e. converting continuous variables to dichotomous variables) and categorizing all dropouts as treatment failures. We will use this approach in analyses for aims 1 and 2. For the continuous variables in the secondary outcomes, we will use BOCF as the most conservative approach. Sensitivity analyses will compare results of our BOCF analysis with that obtained using LOCF or multiple imputation methods. All results will be interpreted and reported after taking into account the results of the sensitivity analyses, applying the principle put forth by the EMA to not favor the “experimental” arm, which in this RCT would be the SCD.

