Similar methods will be employed for reviewing the participating sites regulatory binder. We will provide each site with an electronic storage area where their regulatory documents can be stored and then reviewed by the monitors. Eligibility criteria and consent process will be monitored for all participants. If deemed necessary, on site monitoring will be employed.

Source Documents that will be reviewed by the study monitors for protocol compliance are outlined in the following table.

Data type	Source Document to review
Age	Demographics from medical record
Medications	Office notes from 16 weeks prior to randomization and medication list up to 16 weeks prior to randomization
Clostridium Difficile	Any stool sample testing in medical record within 4 weeks prior to the screening visit
Diabetes Mellitus requiring medication	Medication list and problem list/diagnosis list in medical record
hsCRP	Blood draw results done by the study at the screening visit, at week 6 and week 12
Albumin	Blood draw results in medical record within 4 weeks prior to the screening visit
BMI	Physical exam source document done at the screening visit
FCP	FCP result done by the study at baseline (stool

	must be collected within 28 days prior to start of study diet), at week 6 and week 12
sCDAI score	sCDAI score in the DMS at baseline from at least 5 days of symptom recording
Intestinal Stricture	Imaging in the last year and two office notes – the office note closest to the screening visit and the office note immediately preceding that visit

Data quality checks will be built into the DMS, such that nonsensical data will prompt the Site Coordinators to check for accuracy, certain questions will be required for form completion, and skip patterns will be in place. We will also implement a data quality monitoring system after the second patient is enrolled that will report on form completeness and on the timeliness of form completion. Data quality checks will continue monthly throughout the study by the Data Coordinating Center. Data queries will be sent from the DCC to the local sites.

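### The within-arm sCDAI, PRO2 and PRO3 tests use the score that selected participants as their baseline, so regression to the mean makes the null of no change false even without a diet effect

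*Combined protocol and SAP*

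**What the plan says.** The Study Summary sets entry at sCDAI "sCDAI >175 and <400"; Protocol 4.1 and 4.2 set the same limits. Protocol 6.2.2 gives the data behind the score: "A minimum of 5 and maximum of 7 days of patient reported symptoms will be required to compute the sCDAI to determine eligibility". Protocol 3.2.1 gives the timing: "The participant must complete 5 to 7 days of sCDAI symptom recording (the daily online surveys) before randomization and the start of study diet".

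The plan treats these days as the baseline. Protocol 6.5 lists as a ground for withdrawal before randomisation "Failure to complete at least 5 of the 7 baseline sCDAI surveys". In Appendix C, section 5, the document that monitors check for the eligibility score is the "sCDAI score in the DMS at baseline from at least 5 days of symptom recording". The schedule in 6.1 shows one sCDAI entry before the diet and none at week 0. No second baseline is defined.

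For continuous measures, naming sCDAI, PRO2, PRO3 and fecal calprotectin (FCP), Protocol 8.4.2 says "we will compare the week 6 and week 12 values to the baseline value using the Wilcoxon sign rank test", and then "These analyses will be conducted separately for each treatment group". SAP 5.5.2 repeats this. Both add that missing values in this analysis are imputed as a worsening from baseline, without saying by how much. PRO2 and PRO3 are built from the same diary items (8.2, SAP 5.5.1.3.3). Regression to the mean is not mentioned.

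**The concern.** A one-week symptom score is the participant's usual level plus transient variation. Keeping only people whose score exceeds 175 favours those caught in a bad week, so their next score is expected to be lower whatever they eat. A paired test against the qualifying score therefore tests a null that is false by design. PRO2 and PRO3 inherit the problem through the shared diary days.

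There is no usual-diet arm to absorb this drift. Protocol 7.12 says the indices will be used to judge whether symptoms improved or worsened with the intervention. If the arms do not differ, a significant fall in each could be taken as a sign that the diets helped.

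**Working it through.** **The plan's own figure.** The documents state no error rate or power for the within-arm tests. The relevant design figure is the arm size. For 40% vs 60%, two-sided 5%, 80% power: n = [1.96√(2×0.5×0.5) + 0.8416√(0.24+0.24)]² / 0.2² = (1.386 + 0.583)² / 0.04 = 96.9, so 97 per arm, as in SAP 5.2.

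**Inputs.** From the documents: selection between 175 and 400, signed-rank test, 97 per arm. Assumed, because the documents do not give them: normal scores among those screened with SD 70 and mean μ of 175 to 250, correlation ρ of 0.6 to 0.9 between the qualifying window and week 6, stable disease and no diet effect. The two-sided 5% level is also assumed; the plan states it for the design and primary analysis, not for these tests. The CDAI-with-sCDAI correlations in 8.1 are not test-retest values and cannot be used.

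**Spurious fall.** Expected fall = (1 − ρ) × (mean of those selected − μ). Each cell gives the fall in points, then the simulated share of 97-person arms showing significant improvement (1,500 trials per cell, complete data, nominal 2.5%).

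| Screened mean | Mean of selected | ρ 0.6 | ρ 0.7 | ρ 0.8 | ρ 0.9 |
|---|---|---|---|---|---|
| 175 | 230.6 | 22.2; 95% | 16.7; 86% | 11.1; 69% | 5.6; 39% |
| 200 | 240.4 | 16.1; 73% | 12.1; 60% | 8.1; 44% | 4.0; 23% |
| 225 | 252.0 | 10.8; 40% | 8.1; 32% | 5.4; 23% | 2.7; 13% |
| 250 | 265.3 | 6.1; 17% | 4.6; 14% | 3.1; 10% | 1.5; 7% |

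**Hand check of one cell (μ 200, ρ 0.7).**
- Fall: 0.3 × 40.4 = 12.1. SD of the change: √[(70√(1−0.49))² + (0.3×47.5)²] ≈ 52, where 47.5 is the SD of the selected scores.
- P(change < 0) = Φ(12.1/52) = 0.592. P(sum of two changes < 0) = Φ(√2 × 0.233) = 0.629.
- Expected negative rank sum: 97×0.592 + 4,656×0.629 ≈ 2,986. Under the null it is 97×98/4 = 2,376.5, with SD √(97×98×195/24) = 277.9.
- Expected z = (2,986 − 2,376.5)/277.9 = 2.19, so the test is positive with probability Φ(2.19 − 1.96) ≈ 59%, in line with the simulated 60%.

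**PRO2 and PRO3.** Assuming correlations of 0.7 and 0.9 with sCDAI in the same window, SD 60 and ρ 0.5 to 0.9, false improvement is 18% to 93% at screened mean 180, 9% to 41% at 220 and 3.7% to 9.5% at 260.

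**Effect of the imputation rule (same cell).**
- 10 of 97 missing, ranked as the largest worsenings: expected negative rank sum 87×0.592 + 3,741×0.629 ≈ 2,405; z = 0.10; false improvement about 3%.
- The same 10 ranked as the smallest worsenings: add 10×87×0.592 = 515, giving 2,920; z = 1.95; about 50%.
- 19 missing, ranked largest: negative rank sum 78×0.592 + 3,003×0.629 ≈ 1,935, so the positive sum is 4,753 − 1,935 = 2,818; z = 1.59 towards worsening, and the test declares deterioration in about 36% of trials.

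**Between-arm check.** With the same selection and no effect (μ 220, SD 60, ρ 0.7), a chi-square test on week-6 sCDAI below 150 rejects in 4.5% of trials, so the randomised comparison keeps its level.

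**The case against.** **The size is not known.** This stands. Participants are pre-screened for nominal eligibility, and some are identified by self-reported symptoms (3.2.1), so screened scores may lie well above 175. At a screened mean of 260 (SD 60 or 80, ρ 0.5 to 0.9) false sCDAI improvement is only 4.7% to 15%. A reader might take the high percentages in the table as the trial's error rate; the documents support no single figure.

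**The imputation is conservative.** It pulls the other way, and with enough missing data it removes or reverses the inflation. But it is a second bias of unstated size and does not correct the first.

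**These tests are secondary.** Section 2 calls the secondary aims exploratory, the objectives are comparative, and 12.4 interprets the result only as superiority or not. A reader might infer that the plan will use within-arm p-values to claim that both diets work, or that these tests are its only account of each arm's change. Neither is supported: no passage makes that claim, and the plan also reports the proportion of each group with a PRO2 or PRO3 fall equivalent to 100 CDAI points. The case for changing the tests is that they are specified and their p-values would mislead.

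**A re-measured baseline would solve it.** It is tempting, since 3.2 says "Participants will complete brief daily online surveys throughout their entire study participation, from consent to week 12". Three things stand against relying on it. Section 3.2.1 caps the gap between recording and diet start at 14 days but sets no minimum, so spare days may not exist. Participants learn their open-label assignment before the first meal. And the nominal rate returns only if errors in the two pre-diet windows are independent. If adjacent windows correlate 0.85 and week 6 correlates 0.7, the remaining fall at mean 200 is (0.85 − 0.70) × 40.4 = 6.1 points, with false improvement in about 20% of trials.

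**Conclusion.** The concern holds for the within-arm tests of sCDAI, PRO2 and PRO3. That the null is false with complete data follows from the design and needs only that the diary score varies between weeks. The size rests on the assumed mean, SD and correlation: a fall of about 1.5 to 22 points and false sCDAI improvement in about 7% to 95% of trials over the range in the table. Missing data under the plan's imputation rule can move the rate below nominal or turn the result into a false worsening, so the error rate is uncontrolled in either direction.

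It does not extend to the primary endpoint or any randomised between-arm comparison, because both arms are selected alike. Nor does it extend to FCP, which is not an entry criterion.

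**What to change.** In Protocol 8.4.2 and SAP 5.5.2:

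- Replace the within-arm signed-rank tests of sCDAI, PRO2 and PRO3 with descriptive reporting: change at weeks 6 and 12 in each arm, as an estimate with an interval and no p-value.
- State that this change includes regression to the mean from selection on the baseline score and is not evidence that a diet works.
- State that inference on these measures rests on the randomised between-arm contrast.
- Optionally, add a sensitivity analysis whose baseline is the score from diary days after the qualifying window and before randomisation, in participants with at least 5 such days, using the existing scaling for short windows. Say that this reduces the bias but may not remove it.

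The cost is wording only; no data, visits or participants are added. The plan loses its within-arm significance tests for these three measures.

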**Investigational Product (drug, biologic, device, etc.)**

Specific Carbohydrate Diet – up to 3000 calories provided to the participant per day.

